#### 9.9.2.1. Renal Artery Stenosis Evaluation at 12 Months

With an expected rate of 3.1% for renal artery stenosis at 12 months [7], a sample size of 100 subjects will provide a 95% confidence interval of approximately (0.6%, 8.5%) using the exact method (calculated using an event rate of 3/100=3%).

Descriptive statistics of this endpoint at 12 months will be provided using counts, percentages and the 95% confidence interval.

#### 9.9.3. Primary Efficacy Endpoint

The primary efficacy endpoint of the study is the baseline adjusted (analysis of covariance/ANCOVA) change in SBP from baseline (screening visit 2) to 3-months post-procedure as measured by 24-hour Ambulatory Blood Pressure Monitoring (ABPM).

In the context of an ANCOVA linear regression model,  $\mu = \mu_t - \mu_c$  represents the baseline-adjusted treatment effect of BP change comparing RDN and control groups where  $\mu_t$  and  $\mu_c$  are the baseline adjusted BP changes in the RDN and control groups respectively. Let  $\mathbf{y} = \{\mathbf{y_t}, \mathbf{y_c}\}$  and  $\mathbf{y_0} = \{\mathbf{y_{0t}}, \mathbf{y_{0c}}\}$  represent the pivotal data and prior data respectively, where t = RDN and c = control group. Let the hypotheses for the study be the following:

$$H_0: \mu = 0$$

$$H_a$$
:  $\mu < 0$ 

We reject  $H_0$  if the probability is greater than 97.5%, i.e.

$$P(\mu < 0 | y, y_0, \widehat{\alpha_0}(y, y_0, \lambda, k)) > 0.975$$

where the notation  $\widehat{\alpha_0}(y,y_0,\lambda,k)$  is used to denote that the estimate of  $\widehat{\alpha_0}$  depends on the pivotal data, prior data, and the Weibull shape and scale parameters. In conjunction with a pre-specified decision rule controlling the prior data weight, the estimate of  $\widehat{\alpha_0}(y,y_0,\lambda,k)$  represents a measure of similarity between pivotal and prior data. Alternatively, in the absence of  $\widehat{\alpha_0}(y,y_0,\lambda,k)$ , i.e.,  $P(\mu<0|y,y_0)$ , full weight would be given to the prior data.

### 9.9.4. Primary Efficacy Endpoint Analysis

The power prior discount function approach is used to estimate  $\mu$ , and determine  $\widehat{\alpha_0}(\boldsymbol{y},\boldsymbol{y_0},\lambda,k)$ , the strength of the prior data used to estimate  $\mu$ .  $\widehat{\alpha_0}(\boldsymbol{y},\boldsymbol{y_0},\lambda,k)$  ranges from 0 to 1, where 1 means that 100% of the prior data is used and 0 means that no prior data is used. Before beginning the study, an initial value is chosen for  $\widehat{\alpha_0}(\boldsymbol{y},\boldsymbol{y_0},\lambda,k)$ , call this value  $\alpha_{max}$ . This  $\alpha_{max}$  value is the maximum strength the prior data can receive. We intend to use the same enrollment criteria for the prior and pivotal studies, and therefore believe that a value of  $\alpha_{max}=1$  is appropriate.

At interim looks and at the final analysis, we analyze the data using the power prior discount function method, this method will discount  $\alpha_{max}$  to an appropriate value  $\widehat{\alpha_0}(y,y_0,\lambda,k)$  where  $\widehat{\alpha_0}(y,y_0,\lambda,k) \le \alpha_{max}$ . This discounting is based on the discount function which is discussed in detail in the next section.

Under the adaptive procedure, if the pivotal data diverges from the prior data at an interim look, the discount function will discount the strength of the prior data, thus requiring continued enrollment to maintain power to achieve the endpoint. Alternatively, if the prior and pivotal data agree, there will be a smaller penalty from the discount function, thus fewer prospective patients would be needed to maintain power, and enrollment may stop early.

The ITT population defined in section 9.1.3.1. will be used as the primary analysis population for this endpoint. Secondary effectiveness analyses will also be performed using the modified ITT, per-protocol and as treated populations defined in sections 9.1.3.2., 9.1.3.3. and 9.1.3.4.

#### 9.9.4.1. Discount Function Estimation Method

The power prior discount function method is comprised of four steps: **Compare, Discount, Combine, and Estimate.** 

#### Compare:

We start by stochastically comparing pivotal data vs prior data as follows.

For each treatment group, we separately fit the model to the combined prior and pivotal data:

$$y_i = \tilde{\beta}_0 + \tilde{\beta}_1 I(i \in \text{prior}) + \tilde{\beta}_2 x_i + \varepsilon_i, \quad \varepsilon_i \sim N(0, \tau^2),$$

where  $I(i \in \text{prior}) = 1$  if the subject is from the prior dataset, and 0 otherwise,  $y_i$  is the BP change for the ith observation and  $x_i$  is the mean centered baseline BP for the ith observation. With flat priors on each parameter, we estimate the posterior probability that  $\tilde{\beta}_1 > 0$  by first computing, using Monte Carlo sampling

$$p^* = P[\tilde{\beta}_1 > 0 \mid \mathbf{y}, \mathbf{y}_0].$$

Having calculated this separately for both the RDN  $(p_t^*)$  and control groups  $(p_c^*)$ , they are transformed to  $p_t$  and  $p_c$  using

$$p = \begin{cases} 2p^*, & p^* \le 0.5\\ 2(1-p^*), & p^* > 0.5 \end{cases}$$

Now, under this transformation, if  $p_t$  or  $p_c$  are close to 0, there is a high probability that the pivotal data and prior data come from different populations and discounting should be applied to reduce the influence of the prior. On the other hand, if  $p_t$  or  $p_c$  are close to 1, there is a high probability that the pivotal data and prior data come from similar populations and minimal discounting should be applied.

#### **Discount:**

[figure not shown]
We discount  $\alpha_{max}$  based on the value of  $p_t$  and  $p_c$  from the **Compare** step and the discount function F(p),

$$\widehat{\alpha_0} = \alpha_{max} F(p)$$

where F(p) is a function between 0 and 1. A two-sided Weibull function will be utilized as follows:

$$F(p) = 1 - e^{-\left(\frac{p}{\lambda}\right)^k}$$

For this study, we will be using a shape parameter of k=3 and a scale parameter of  $\lambda=0.5$  (illustrated below). Note that we will use the same Weibull function parameters for both RDN and control groups, but  $p_t$  and  $p_c$  will have different values from the **Compare** step.

#### **Combine:**

Using the power prior method and  $\widehat{\alpha_0}$  we can combine the prior and pivotal data together using Bayesian techniques to construct the posterior distribution for  $\mu$  as follows. We first begin with a hierarchical linear regression model of the form:

$$\begin{array}{lll} y_{i} \mid \mu_{t}, \mu_{c}, \beta, \sigma^{2} & \sim & N(\mu_{t}I(i \in t) + \mu_{c}I(i \in c) + x_{i}\beta, \, \sigma^{2}), \, i = 1, \ldots, n, \\ \mu_{t} \mid \mu_{0t}, \sigma_{0t}^{2}, \widehat{\alpha_{0t}} & \sim & N(\mu_{0t}, \, \sigma_{0t}^{2}/\widehat{\alpha_{0t}}), \\ \mu_{c} \mid \mu_{0c}, \sigma_{0c}^{2}, \widehat{\alpha_{0c}} & \sim & N(\mu_{0c}, \, \sigma_{0c}^{2}/\widehat{\alpha_{0c}}), \\ \beta & \sim & N(\alpha_{\beta}, \, b_{\beta}^{2}), \\ \pi(\sigma^{2}) & \propto & \sigma^{-2}, \end{array}$$

where  $N(\cdot)$  denotes a normal distribution,  $I(\cdot)$  is the indicator function where  $I(i \in t)$  indicates that observation i is in the RDN group and  $I(i \in c)$  indicates observation i is in the control group,  $y_i$  is the BP change for the ith observation,  $x_i$  is the mean centered baseline BP value for the ith observation, and

each of  $\mu_{0t}$ ,  $\mu_{0c}$ ,  $\sigma_{0t}^2$ ,  $\sigma_{0c}^2$  are hyperparameters estimated from the historical data, and  $a_{\beta}=0$  and  $b_{\beta}=10^{10}.10^{10}$ 

To carry out estimation in a computationally efficient manner, we rely on a reparameterization derived in Gelman [4]. First, construction vectors and matrices:  $\mathbf{y} = (y_1, ..., y_n)^T$ ,  $\mathbf{x}_t$  and  $\mathbf{x}_c$  vectors of binary treatment control indicators taking values 0 and 1,  $\mathbf{x}_\beta$  the vector of baseline values,  $\mathbf{X} = (\mathbf{x}_t \mid \mathbf{x}_c \mid \mathbf{x}_\beta)$  the  $n \times 3$  design matrix,  $\mathbf{\theta} = (\mu_t, \mu_c, \beta)^T$  parameters of interest to be estimation. Then, we can write the model as

$$\mathbf{y}_* \sim N(\mathbf{X}_* \boldsymbol{\theta}, \boldsymbol{\Sigma}_*)$$

where  $\mathbf{y}_* = (\mathbf{y}^T, \mu_{0t}, \mu_{0c}, a_{\beta})^T$ ,  $\mathbf{X}_* = (\mathbf{X}^T, \mathbf{I}_3)^T$ ,  $\mathbf{I}_3$  is a  $3 \times 3$  identity matrix, and

$$\mathbf{\Sigma}_* = \begin{pmatrix} \sigma^2 \mathbf{I}_n & 0 \\ 0 & \mathbf{\Sigma}_{\theta} \end{pmatrix},$$

where

$$\mathbf{\Sigma}_{\theta} = \begin{pmatrix} \sigma_{0t}^2/\widehat{\alpha_{0t}} & 0 & 0\\ 0 & \sigma_{0c}^2/\widehat{\alpha_{0c}} & 0\\ 0 & 0 & b_{g}^2 \end{pmatrix}.$$

The posterior mean of  $\theta$  is found via least squares as

$$\widehat{\boldsymbol{\theta}} = (\boldsymbol{X}_{*}^{T} \boldsymbol{\Sigma}_{*}^{-1} \boldsymbol{X}_{*})^{-1} \boldsymbol{X}_{*}^{T} \boldsymbol{\Sigma}_{*}^{-1} \boldsymbol{\gamma}_{*}$$

and the posterior variance of  $\theta$  is

$$\boldsymbol{V}_{\theta} = (\boldsymbol{X}_{*}^{T} \boldsymbol{\Sigma}_{*}^{-1} \boldsymbol{X}_{*})^{-1}.$$

Thus, the posterior distribution of  $\theta$  is  $\theta \mid y_*, \Sigma_* \sim N(\widehat{\theta}, V_{\theta})$ . Both  $\widehat{\theta}$  and  $V_{\theta}$  are composed of an unknown  $\sigma^2$ . The marginal posterior distribution of  $\sigma^2$  is

$$q(\sigma^2 \mid \mathbf{y}) \propto \pi(\sigma^2) |\sigma^2 I_n|^{-\frac{1}{2}} \exp\left\{-\frac{1}{2} (\mathbf{y}_* - \mathbf{X}_* \widehat{\boldsymbol{\theta}})^T \mathbf{\Sigma}_*^{-1} (\mathbf{y}_* - \mathbf{X}_* \widehat{\boldsymbol{\theta}})\right\},$$

which does not have a known distributional form. Here,  $\pi(\sigma^2)$  is the prior distribution of  $\sigma^2$ . Thus, to draw samples from the posterior distribution of  $\sigma^2$ , we rely on a grid search to sample values of  $\sigma^2$ .

We proceed by drawing samples from  $\sigma^2 \sim q(\sigma^2|y)$ . Using these estimates, we input them into the posterior distribution of  $\theta$ . By repeating this process a large number of times, we will be drawing posterior samples from  $\theta$  which will account for the uncertainty in both  $\sigma^2$  as well as appropriately weighting the prior data based on  $\widehat{\alpha_{0t}}$  and  $\widehat{\alpha_{0c}}$ .

We can than construct the following contrast of interest from the drawn samples:

$$\mu = \mu_t - \mu_c$$
.

In the R package bayesDP version 1.3.2, the bdplm function

<sup>10 In the R package bayesDP version 1.3.2, the bdplm function parameter 'prior\_covariate\_sd' is described as "The prior standard deviation(s) of the covariate effect(s). Default value is 1e4." Upon inspection of the code, it appears the standard deviation is internally scaled by 1e6, thus yielding a more diffuse prior for  $\beta$ . Therefore, the actual value of  $b_{\beta}$  used in the analysis is 1e10.

Use of this contrast leads to the univariate distribution of interest concerning the mean BP change difference between the test and control groups.

[figure not shown]

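### The marginal posterior of σ² printed in SAP 9.9.4.1 omits the factor |Vθ|^(1/2); whether the analysis software also omits it is not shown

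*SAP*

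**What the plan says.** SAP 9.9.4.1 (Combine) sets up a normal regression with coefficients θ = (μt, μc, β) and residual variance σ². The discounted prior data enter as normal priors on μt and μc. β has an essentially flat prior, and the prior on σ² is proportional to 1/σ². Given σ², θ is normal with mean θ̂ and variance Vθ = (X∗ᵀ Σ∗⁻¹ X∗)⁻¹, and the SAP notes that θ̂ and Vθ both "are composed of an unknown" σ².

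The section then states the marginal posterior of σ² as "\pi(\sigma^2) |\sigma^2 I_n|^{-\frac{1}{2}} \exp" of minus half the weighted residual sum of squares at θ̂. It describes this as an expression "which does not have a known distributional form" and continues: "we rely on a grid search to sample values of" σ². Each draw of σ² is passed into the normal posterior of θ, and μ = μt − μc is formed from the result. A footnote ties the computation to the package: "In the R package bayesDP version 1.3.2, the bdplm function" is cited for the prior SD of β. The code itself is not reproduced.

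The null hypothesis is rejected "if the probability is greater than 97.5"% (SAP 9.9.3). SAP 9.9.5.1 uses the same rule for office SBP, and it applies at both interim looks and at the final analysis.

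**The concern.** To go from the joint posterior of (θ, σ²) to the marginal of σ², θ has to be integrated out. For a normal θ this leaves a multiple of |Vθ|^(1/2). If Vθ were free of σ² the factor could be dropped as a constant, but the SAP itself says that Vθ contains σ². The printed expression is therefore the joint density evaluated at θ̂. It takes no account of the three coefficients having been estimated.

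σ² sets the posterior SD of μ, and so P[suc], for both powered endpoints at every look. An analysis that followed the printed expression would have a slightly too narrow posterior. The shortfall would be largest when the prior is fully discounted and the pivotal data stand alone.

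**Working it through.** **Inputs.** Looks at n = 210, 240 and 300, allocated 1:1 (SAP 7 and 9.8). For 24-hour SBP: pivotal SD 12; prior SEs 1.65 (RDN) and 1.62 (control) (SAP Table 3). For office SBP, the values in SAP Table 4. Prior on σ² proportional to 1/σ²; three coefficients (SAP 9.9.4.1). Stated power 94% and one-sided type I error 0.029 (24-hour) and 0.026 (office) (SAP Table 5).

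**1. The plan's own figures.** The formula has no number attached, so the nearest check is Table 5. The three-look design was simulated with the printed formula (8,000 trials for power, 60,000 under the null). The endpoint correlation is not given, so 0, 0.5 and 0.8 were tried.

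- Power for both endpoints: 91.8%, 92.4% and 92.9%. For the primary alone: 93.2% in each case.
- Type I error (24-hour/office): 0.027/0.025, 0.030/0.028 and 0.035/0.032.

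The stated values are approached but not matched exactly; the correlation and the null set-up are unknown.

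**2. The missing factor.** Write Q(θ) for the weighted residual sum of squares. Completing the square gives Q(θ) = Q(θ̂) + (θ−θ̂)ᵀ Vθ⁻¹ (θ−θ̂). The integral of exp{−½(θ−θ̂)ᵀ Vθ⁻¹ (θ−θ̂)} over the three coefficients is (2π)^(3/2) |Vθ|^(1/2). Hence

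`q(σ²|y) ∝ π(σ²) |σ² I_n|^(-1/2) |Vθ|^(1/2) exp{-Q(θ̂)/2}`.

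Reducing |Σ∗| to |σ² I_n| is legitimate, because the prior block does not involve σ².

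**3. No borrowing (α̂₀ = 0).** Here |Vθ|^(1/2) ∝ (σ²)^(3/2). The printed form is a scaled inverse chi-square with n degrees of freedom and the correct one has n−3, as in ordinary ANCOVA. With SSE the residual sum of squares, the posterior means are SSE/(n−2) and SSE/(n−5), so the printed value is too small by the ratio (n−5)/(n−2):

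- n=210: 205/208 = 0.9856
- n=240: 235/238 = 0.9874
- n=300: 295/298 = 0.9899

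The SD of μ scales with the square root: √0.9856 = 0.9928 at n=210, which is 0.7% too low.

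**4. With borrowing, n=210.** Near σ² = 144 each arm has data precision 105/144 = 0.729. At α̂₀ = 1 the prior precisions are 1/1.65² = 0.367 and 1/1.62² = 0.381. The degrees of freedom lost are about 1 + 0.729/(0.729+0.367) + 0.729/(0.729+0.381) = 2.32, giving a σ² ratio of (208−2.32)/208 = 0.9888. Grid evaluation agrees:

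| α̂₀ | σ² ratio, printed/correct | SD(μ) ratio |
|---|---|---|
| 0 | 0.9856 | 0.9928 |
| 0.5 | 0.9875 | 0.9950 |
| 1 | 0.9888 | 0.9963 |

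**5. Independent reference.** A Gibbs sampler of the SAP's model, run on one example dataset at n=210 without borrowing, gave E(σ²) = 145.3. The density with the factor gave 145.2 and the printed one 143.1. The 95% interval for μ was 6.517 mmHg wide as printed and 6.564 mmHg with the factor.

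**6. Fixed-sample size, no borrowing.** Under the printed form success requires T > t(0.975; n) × √((n−3)/n), where T is the usual statistic on n−3 degrees of freedom. At n=210 the cut-off is 1.9713 × √(207/210) = 1.9572, and P(t₂₀₇ > 1.9572) = 0.0258. At 240 and 300 the sizes are 0.0257 and 0.0256.

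**7. Effect on the design.** In the simulation of step 1, adding the factor lowers overall power by 0.04 to 0.1 point, look-1 success by about 0.2 point and type I error by 0.0004 to 0.0008. The primary look-1 decision changes in about 0.1% of trials.

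**The case against.** A reader might infer that the trial's intervals were too narrow and its posterior probabilities too high. The documents do not support that. They show an expression, not the code that was run, and the footnote on β's prior SD shows that a description of bdplm and its behavior can differ. If the package includes the factor, no result is affected. This objection stands, and it is why the numerical effect is stated conditionally.

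A second tempting reading is that the efficacy conclusion is in doubt. It is not. Protocol B.1.2 reports that enrollment stopped for efficacy at the first interim analysis, with posterior probability above 0.999 for both powered endpoints. The largest overstatement of P[suc] seen in 60 simulated datasets at n=210 without borrowing was 0.0017. Subtracting it leaves more than 0.999 − 0.0017 = 0.9973, against a threshold of 0.975.

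It is also fair to say that the effect is too small to see in the stated operating characteristics. With 15,000 simulations, the Monte Carlo standard error at 0.029 is √(0.029 × 0.971/15000) = 0.0014, larger than the 0.0004 to 0.0008 found here. If those simulations used the same routine, which the SAP does not say, any effect is already in the stated error rates.

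Finally, some symbols near the formula are garbled in the SAP's text layer (a subscript g appears where β is meant in Σθ). The printed page should be checked, although losing a whole factor is less likely than misreading a character.

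None of this rescues the formula. The algebra follows from the SAP's own model, and someone validating independently from the printed text would either repeat the omission or disagree with a correct program.

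**Conclusion.** As printed, the expression is not the marginal posterior of σ²; the factor |Vθ|^(1/2) is missing. That conclusion needs no assumption beyond the SAP's stated model.

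The numerical consequence holds only if the analysis follows the printed expression. In that case the bias is anti-conservative and small, with the n=210 sizes shown in the working, and it shrinks as n grows. Those sizes assume that 12 mmHg is the residual SD and that baseline is balanced between arms. The operating-characteristic changes also rest on the assumed endpoint correlations, a null set at the control mean, the Compare step done from summary data, and no futility stop (SAP Table 5 puts futility stops at 0.05% of simulations).

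This is a minor correction to the specification. It does not show that any reported analysis is wrong.

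**What to change.** 1. In SAP 9.9.4.1 replace the expression by `q(σ²|y) ∝ π(σ²) |σ² I_n|^(-1/2) |Vθ|^(1/2) exp{-½ (y* - X*θ̂)ᵀ Σ*⁻¹ (y* - X*θ̂)}`.
2. Have the Level 1 validation already required by SAP 10 establish which density bdplm in bayesDP 1.3.2 samples, and record the answer in a footnote, as footnote 10 does for the prior SD of β. A simple test is a run with no prior weight: the posterior mean of σ² should be close to SSE/(n−5), not SSE/(n−2).
3. If the code lacks the factor, keep the original result and report the corrected posterior beside it. Because the efficacy results are known, describe this as a deviation in the Final Clinical Study Report, as Protocol section H provides.

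The cost is one formula and one check. Step 3 would add a rerun of the two powered endpoints.

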#### **Estimate:**

The posterior distribution from the combined prior and pivotal data is used to estimate the posterior probability

$$P(\mu < 0 | \mathbf{y}, \mathbf{y_0}, \widehat{\alpha_0}(\mathbf{y}, \mathbf{y_0}, \lambda, k))$$
 (1)

where the notation  $\widehat{\alpha_0}(y,y_0,\lambda,k)$  is used to denote that the estimate of  $\widehat{\alpha_0}$  depends on the pivotal data, prior data, and the Weibull shape and scale parameters. In conjunction with a prespecified decision rule controlling the prior data weight, the estimate of  $\widehat{\alpha_0}(y,y_0,\lambda,k)$  represents a measure of similarity between pivotal and prior data. Alternatively, in the absence of  $\widehat{\alpha_0}(y,y_0,\lambda,k)$ , i.e.,  $P(\mu<0|y,y_0)$ , full weight would be given to the prior data.

[figure not shown]
The blue dashed line in the figure below is an illustrative example of the estimate from pivotal data (black) and prior data (red).

The analysis in (1) is performed at all interim looks and at the final analysis.

#### 9.9.4.2. Illustration of Discount Function Scenarios

The Figure below shows how the discount function operates with hypothetical data sets

The panels in this figure can be interpreted as follows:

- Top panel: The pivotal (current) data is very similar to the prior. The discount function allows for full strength of the prior. The posterior (final estimate) is a balance between the prior and pivotal study.
- Middle panel: The pivotal (current) data is similar to the prior. The discount function penalty is moderate, resulting in a prior effective sample size of 17 out of a max of 50. Because the agreement is reasonable, the posterior (final estimate) is similar to both the prior and pivotal study.
- Bottom panel: The pivotal (current) data shows lower performance than the prior. The discount function produces a substantial penalty resulting in no weight to the prior. The posterior (final estimate) is essentially the same as the pivotal (current) study.

## 9.9.5. Secondary Efficacy Objectives

#### 9.9.5.1. Powered Secondary Efficacy Endpoint

The secondary powered efficacy endpoint is the baseline adjusted change in office SBP from baseline (screening visit 2) to 3-months post procedure, compared between treatment groups.

In the context of an ANCOVA linear regression model,  $\mu = \mu_t - \mu_c$  represents the baseline-adjusted treatment effect of BP change comparing test and control groups where  $\mu_t$  and  $\mu_c$  are the baseline adjusted BP changes in the RDN and control groups respectively. Let  $\mathbf{y} = \{\mathbf{y}_t, \mathbf{y}_c\}$  and  $\mathbf{y}_0 = \{\mathbf{y}_{0t}, \mathbf{y}_{0c}\}$  represent the pivotal data and prior data respectively, where the subscripts t = RDN group and c = control group. Let the hypotheses for the study be the following:

$$H_0: \mu = 0$$

$$H_a$$
:  $\mu < 0$ 

We reject  $H_0$  if the probability is greater than 97.5%, i.e.

$$P(\mu < 0 | y, y_0, \widehat{\alpha_0}(y, y_0, \lambda, k)) > 0.975$$

where the notation  $\widehat{\alpha_0}(y,y_0,\lambda,k)$  is used to denote that the estimate of  $\widehat{\alpha_0}$  depends on the pivotal data, prior data, and the Weibull shape and scale parameters. In conjunction with a pre-specified decision rule controlling the prior data weight, the estimate of  $\widehat{\alpha_0}(y,y_0,\lambda,k)$  represents a measure of similarity between pivotal and prior data. Alternatively, in the absence of  $\widehat{\alpha_0}(y,y_0,\lambda,k)$ , i.e.,  $P(\mu<0|y,y_0)$ , full weight would be given to the prior data.

The same statistical methods as outlined in section 9.9.4 will be used to analyze the powered secondary endpoint. The ITT population defined in section 9.1.3.1. will be used as the primary analysis population for this endpoint. Secondary effectiveness analyses will also be performed using the modified ITT, perprotocol and as treated populations defined in sections 9.1.3.2., 9.1.3.3. and 9.1.3.4.

# 9.9.6. Simulation of Primary and Secondary Efficacy Endpoint Operating Characteristics

As outlined in section 7.8 enrollment will be stopped at an interim analysis for efficacy or futility only if both the primary and secondary efficacy endpoints meet the stopping criteria. Simulations were performed to assess operating characteristics for the primary and secondary efficacy endpoints. We used 8000 trial simulations to estimate the power and 15000 simulations to estimate the type I error. Tables 3 and 4 summarize the assumptions that were made for the primary and secondary efficacy endpoint simulations, and table 5 summarizes the operating characteristics for the efficacy evaluation. The overall power for the efficacy evaluation from table 5 is 94%, with a one-sided type I error rate of 0.029 for 24-hour SBP and 0.026 for Office SBP.

